9.9. Study Medication Accountability

9.9.1. Handling of Study Medications

The Investigator shall take adequate precautions, including storage of the study medications in a securely locked, substantially constructed cabinet or other securely locked, substantially constructed enclosure (or a locked refrigerator for CST-2032), access to which is limited, to prevent theft or diversion of the substances into illegal channels of distribution.

9.9.2. Disposition of Study Medications

The Investigator is required to maintain adequate records of the disposition of the study medications, including dates, quantity, and use by subjects. If the investigation is terminated, suspended, discontinued, or completed, the Investigator shall return the unused supplies to the Sponsor or designee or dispose in accordance with established site procedures. When the Sponsor has indicated in writing that study medication is to be destroyed on site, destruction must be in accordance with local regulations for the product type and a destruction certificate must be provided to the Sponsor.

9.10. Confidentiality

All clinical trial findings and documents will be regarded as confidential. The Investigator and members of his/her research team must not disclose such information without prior written approval from the Sponsor.

The anonymity of participating subjects must be maintained, and national requirements and guidelines must be followed. Subjects will be identified on eCRFs and other documents by their subject number, sex and/or birth date, not by name and subject to local requirements. Documents that identify the subject (e.g., the signed informed consent) must be maintained in confidence by the Investigator.

9.11. Publication Policy

By signing the clinical trial protocol, the Investigator agrees with the use of results of the clinical trial for the purposes of national and international registration, publication, and information for medical and pharmaceutical professionals. If necessary, the authorities will be notified of the Investigator's name, address, qualifications, and extent of involvement.

All information not previously published concerning CST-2032 and/or CST-107 and the Sponsor's operations, including, but not limited to, patent applications, formulas, manufacturing processes, basic scientific data, and formulation information, supplied by the Sponsor to the Investigator is considered confidential and shall remain the sole property of Sponsor. The Investigator agrees to use and maintain the confidentiality of this information in accordance with the provisions contained in the clinical trial agreement. Any use or reproduction thereof, including, but not limited to, publications or presentations by the Investigator or his/her associates, must be submitted to the Sponsor for review and approval in accordance with the provisions contained in the relevant agreement governing the conduct of this trial. All publications must acknowledge the sponsorship of Sponsor.

1 ABBREVIATIONS

ADCS-CGIC	Alzheimer's Disease Cooperative Study-Clinical Global Impression of Change
APOE4	Apolipoprotein E4
β-AR	Beta-adrenoceptor
β-hCG	Beta human chorionic gonadotropin
AD	Alzheimer's Disease
AE	Adverse event
ADHD	Attention Deficit/Hyperactivity Disorder
AS	Apathy scale
ATT	Adaptive tracking test
AUC _{inf}	Area under the drug concentration-time curve from time zero to infinity
AUC _t	Area under the drug concentration-time curve from time zero to time t
BMI	Body mass index
BP	Blood pressure
CAARS	Connors Adult Attention Deficit/Hyperactivity Disorder Scale – short form, self-report
cAMP	cyclic adenosine monophosphate
CANTAB	Cambridge Neuropsychological Test Automated Battery
CBF	Cerebral blood flow
cGCP	Current Good Clinical Practice
C _{max}	Maximum concentration
CNR	Contrast-to-noise ratio
CNS	Central nervous system
CRF	Case report form
C-SSRS	Columbia-Suicide Severity Rating Scale
CST-107	Nadolol
DSMB	Data and Safety Monitoring Board
DSM-V	Diagnostic and Statistical Manual of Mental Disorders 5
DSST	Digital Symbol Substitution Test
EC	Ethics Committee
eCRF	Electronic case report form
ECG	Electrocardiogram
EW	Early withdrawal
FAS	Full analysis set
FERT	Facial Expression Recognition Task
FSH	Follicle-stimulating hormone
GBA	Glucocerebrosidase (GCase) protein
GDS-30	Geriatric Depression Scale – 30 questions
HR	Heart rate
HbsAb	Hepatitis B surface antibody
HbsAg	Hepatitis B surface antigen
HCV Ab	Hepatitis C antibody
HIV	Human immunodeficiency virus
IB	Investigator Brochure
ICF	Informed consent form
ICH	International Council for Harmonisation

ICSD-3	International Classification of Sleep Disorders, Third Edition
IRB	Institutional review board
ISI	Interstimulus interval
ITT	Intent to treat
IV	Intravenous
IWRS	Interactive Web Response System
LC	Locus coeruleus
LRRK2	Leucine rich repeat kinase 2
MAOI	Monoamine oxidase inhibitor
MCI	Mild cognitive impairment
MD	Mild Dementia
MedDRA	Medical Dictionary for Regulatory Activities
MHYS	Modified Hoehn & Yahr Scale
MoCA	Montreal Cognitive Assessment
PAL	Paired Associates Learning
PD	Parkinson's Disease
PI	Principal Investigator
PK	Pharmacokinetic
PKS	PK set
PO	By mouth/oral administration
PPS	Per protocol set
pVFT	Phonological verbal fluency test
QD	Once daily
QTcF	QT interval corrected for changes in heart rate using the Fridericia equation
RBD	REM Sleep Behavior Disorder
RBD1Q	REM Sleep Behavior Disorder Single-Question Screen
RTI	Reaction Time Index
SAE	Serious adverse event
SAP	Statistical analysis plan
SARS-CoV-2	Severe acute respiratory syndrome coronavirus 2
SAS-6	Starkstein apathy scale – short form (6 questions)
SIR	standard image recognition
SNRI	serotonin/noradrenaline reuptake inhibitors
SOP	Standard operating procedure
SSRI	Serotonin selective reuptake inhibitors
SST	Stop signal test
$t_{1/2}$	Time to maximum observed drug concentration
TEAE	Treatment emergent adverse event
t_{max}	Time of maximum concentration
VRM	Verbal Recognition Memory
WAIS-IV	Wechsler Adult Intelligence Scale, Fourth Edition

2 INTRODUCTION

The statistical analysis plan (SAP) details the planned statistical analysis methods required to address the study objectives as described in CuraSen's protocol CST2032/CST-107-CLIN-015: A Phase 2a, Randomized, Placebo-Controlled, Double-Blind, Crossover Study to Evaluate the Safety, Tolerability and Effects of CST-2032 and CST-107 on Cognition in Subjects with Mild Cognitive Impairment or Mild Dementia due to Parkinson's or Alzheimer's Disease.

This SAP should be read in conjunction with the study protocol, case report form (CRF), and any other applicable study documents. This version of the SAP is based on the protocol CST2032-CST107-CLIN-015, Amendment 10 dated 11Jul2023 and CRF version 7.0 dated 31Mar2023. Changes to these documents may result in subsequent changes to the SAP. The final, sponsor-approved version of the SAP must occur prior to database lock.

2.1 Changes to the Planned Analysis

There is still no adjustment of Type I error but hypotheses are not designated in priority order for hierarchical testing.

3 STUDY OBJECTIVES AND ENDPOINTS

Objectives	Endpoints
Primary The primary objective of this study is to evaluate the safety and tolerability of CST-2032 when combined with CST-107.	The primary endpoint is safety and tolerability of CST-2032 including adverse event rates (AEs), serious adverse event rates (SAEs), study discontinuation rates, electrocardiograms (ECGs), vital signs, and laboratory safety observations.
Secondary The secondary objectives of this study will evaluate the effects of CST-2032 when combined with CST-107 versus placebo on the following measures: 
1. Cognition2. Mood3. Attention Deficit4. Apathy5. Overall clinical improvement6. PK	The secondary endpoints will compare the effect of CST-2032 administered with CST-107 versus placebo on the following: 
• Cognitive tasks in the Cambridge Neuropsychological Test Automated Battery (CANTAB) and other cognitive measures:
○ Reaction Time (RT) – attention○ Verbal Recognition Memory (VRM) – episodic memory (verbal stimuli)○ Adaptive Tracking Task (ATT) – visuospatial with strong attentional demand○ Paired Associates Learning (PAL) – episodic memory (visual stimuli)

	
○ Delayed Verbal Recall – episodic memory (verbal stimuli)○ Stop Signal Task (SST) – response inhibition (impulsivity), an aspect of executive function○ Phonological verbal fluency (pVFT)○ Digit symbol substitution test (DSST)○ Color Trails Test (select sites only)● Facial expression recognition task (FERT).● Geriatric Depression Scale – 30 questions (GDS-30).● Conners Adult Attention Deficit Hyperactivity Disorder (ADHD) Rating Scale, short form, self-report (CAARS).● Starkstein Apathy scale short form (SAS-6).● Alzheimer's Disease Cooperative Study-Clinical Global Impression of Change (ADCS-CGIC).● Suicidal ideation using the Columbia Suicide Severity Rating Scale (C-SSRS).● Plasma pharmacokinetics (PK) parameters of CST-2032 and CST-107 (including C_{max}, t_{max}, AUC_t, $t_{1/2}$).
--	--

Exploratory

The exploratory objectives are:

- To evaluate whether baseline disease characteristics impact response to treatment.
- To characterize the effects of treatment on neurodegenerative biomarkers in the blood such as neurofilament light chain, total and phosphorylated tau protein, and amyloid- β (A β) peptides may also be measured.

The following exploratory endpoints may be undertaken to evaluate:

- Subgroup and/or correlation analyses of effects of treatment on baseline disease characteristics including but not limited to disease activity as determined from relevant disease scales at screening, genetic variants involved in neurodegenerative disease including but not limited to apolipoprotein E4 (APOE4), leucine rich repeat linase2 (LRRK2), and glucocerebrosidase (GCase) protein

	
(GBA) (optional and where applicable).
 
• Changes in neurodegenerative biomarkers, such as neurofilament light chain, total and phosphorylated tau protein, and amyloid-β (Aβ) peptides, as measured prior to and after treatment may be evaluated.• Change in average z-score for baseline-deficit cognitive tasks identified for each subject from the Cognitive tasks in the Cambridge Neuropsychological Test Automated Battery (CANTAB) and other cognitive measures.
--	---

4 STUDY DESIGN

4.1 General Description

This is a Phase 2a, randomized, placebo-controlled, double-blind crossover study to evaluate the safety, tolerability and effects CST-2032 administered with CST-107 on cognition in subjects with MCI or mild dementia.

Approximately 60 subjects will be enrolled in a 2 period, 2-way crossover design following study eligibility confirmation during the screening period.

During each treatment period, subjects will receive 3 mg CST-107 or matching placebo on Day -1, followed by daily doses of 3 mg CST-2032 (co-administered with 3 mg CST-107) or matching placebo on Day 1 through Day 14. The study medications will be provided as oral tablets for CST-2032, CST-107, and corresponding matching placebos. Each treatment period will be separated by a washout period of at least 7 days and up to 21 days.

[figure not shown]
All subjects will complete clinical, cognitive and pharmacodynamic assessments during each treatment period as indicated in the Scheduled of Events in Appendix 2 of this SAP.

PK blood samples will be collected prior to, during and after study medication administration, as indicated in the Schedule of Events.

The study duration will be approximately 12 weeks, which includes a Screening period of up to 28 days, the treatment/study period of 7 weeks (two 2-week treatment periods separated by a washout period of at least 7 and up to 21 Days), and the End-of-Study Visit of up to 12 Days after the last study drug dose.

Subjects will be enrolled at up to 20 clinical sites in the USA and New Zealand.

Study Schema

Cognition tests to include (CANTAB), phonological verbal fluency test (pVFT), digit symbol substitution test (DSST).

*Secondary endpoint measures include facial expression recognition task (FERT); Geriatric Depression Scale – 30 questions (GDS-30); Conners Adult Attention Deficit Hyperactivity Disorder Scale (ADHD) Rating Scale, short form, self-report (CAARS); Starkstein Apathy scale short form (SAS-6); and Alzheimer's Disease Cooperative Study-Clinical Global Impression of Change (ADCS-CGIC). ADCS-CGIC is not done on Day -1 or Day 1.

4.2 Randomization and Blinding

The designated Interactive Web Response System (IWRS) will be used to randomize subjects into the study on Day -1. Eligible subjects will be randomly assigned in a 1:1 ratio to one of the following 2 treatment regimens/sequences:

	Treatment Period 1	Treatment Period 2
1	3 mg CST-2032 + 3 mg CST-107	Placebo (2032) + placebo (107)
2	Placebo (2032) + placebo (107)	3 mg CST-2032 + 3 mg CST-107

The IWRS will provide the randomization number.

This clinical trial is a double-blinded study, with the Sponsor, subjects, and site personnel (e.g., study nurses, coordinators, investigators) blinded to treatment assignment. Limited staff will have access to treatment assignments, such as the unblinded statistical team, IWRS system administration, and drug supply management team.

CST-2032 matched placebo and CST-107 matched placebo will be packaged and color-, size-, and shape-matched to be indistinguishable from CST-2032 3 mg and CST-107 3 mg.

4.3 Sample Size

A total of approximately 60 subjects is planned. Although formal hypothesis testing is planned, the study is underpowered for detecting meaningful cognitive benefits and lack of significance will not be interpreted as lack of a treatment effect. The sample size is based on practical considerations and is typical of studies whose objectives are to evaluate the safety and cognitive effects of a therapeutic intervention.

4.4 Study Committees

4.4.1 Data and Safety Monitoring Board

A Data and Safety Monitoring Board (DSMB) will be established to assess participant safety at predetermined intervals (including an optional interim analysis) during the study as needed. Further details will be provided in the DSMB Charter.

4.5 Timing of Analyses

An unblinded interim analysis may be conducted after approximately 50% of subjects have completed Treatment Period 1. A subset of the analysis will be reviewed in closed DSMB sessions and all results will be reviewed by the unblinded CuraSen team. Results reviewed by the DSMB are marked in the table below with asterisks. All efforts will be made by data management to clean the data as much as possible for this analysis. It is expected that the following set of 24 outputs will be generated:

Number	Title	Population
14.1.1*	Subject Disposition	Intent to Treat Set
14.1.2*	Demographics and Baseline Characteristics	Intent to Treat Set
14.2.2.1.1*	Secondary Endpoint: CANTAB Observed and Change from Baseline Results by Timepoint	Full Analysis Set
14.2.2.1.2	Secondary Endpoint: CANTAB Observed and Change from Baseline Results by Timepoint – Subgroup Analysis	Full Analysis Set
14.2.2.1.3*	Secondary Endpoint: CANTAB Observed and Change from Baseline Results by Timepoint during Treatment Period 1	Full Analysis Set
14.2.2.1.4*	Secondary Endpoint: CANTAB Observed and Change from Baseline Results by Timepoint during Treatment Period 2	Full Analysis Set
14.2.2.1.5*	Secondary Endpoint: CANTAB Observed and Change from Baseline Results by Timepoint	Per Protocol Set
14.2.2.1.6	Secondary Endpoint: CANTAB Observed and Change from Baseline Results by Timepoint – Subgroup Analysis	Per Protocol Set
14.2.2.1.7*	Secondary Endpoint: CANTAB Observed and Change from Baseline Results by Timepoint during Treatment Period 1	Per Protocol Set
14.2.2.1.8*	Secondary Endpoint: CANTAB Observed and Change from Baseline Results by Timepoint during Treatment Period 2	Per Protocol Set

14.2.2.2.1*	Secondary Endpoint: Verbal Fluency Test Observed and Change from Baseline Results by Timepoint	Full Analysis Set
14.2.2.2.2	Secondary Endpoint: Verbal Fluency Test Observed and Change from Baseline Results by Timepoint – Subgroup Analysis	Full Analysis Set
14.2.2.3.1*	Secondary Endpoint: Digital Symbol Substitution Test Observed and Change from Baseline Results by Timepoint	Full Analysis Set
14.2.2.3.2	Secondary Endpoint: Digital Symbol Substitution Test Observed and Change from Baseline Results by Timepoint – Subgroup Analysis	Full Analysis Set
14.2.2.9.1*	Secondary Endpoint: Montreal Cognitive Assessment Observed and Change from Baseline Results by Timepoint	Full Analysis Set
14.2.2.9.2	Secondary Endpoint: Montreal Cognitive Assessment Observed and Change from Baseline Results by Timepoint – Subgroup Analysis	Full Analysis Set
14.3.1.1*	Overall Summary of Adverse Events	Safety Set
14.3.1.2*	Treatment-Emergent Adverse Events by System Organ Class and Preferred Term	Safety Set
14.3.1.3*	Treatment-Emergent Serious Adverse Events by System Organ Class and Preferred Term	Safety Set
14.3.4.1.1*	Hematology – Observed Results and Change from Baseline by Timepoint	Safety Set
14.3.4.2.1*	Clinical Chemistry – Observed Results and Change from Baseline by Timepoint	Safety Set
14.3.4.2.2	Clinical Chemistry – Shifts from Baseline by Timepoint	Safety Set
14.3.5.1*	Vital Signs – Observed Results and Change from Baseline by Timepoint	Safety Set
14.3.6.1*	Electrocardiogram (ECG) – Observed Results and Change from Baseline by Timepoint	Safety Set

* denotes outputs to be reviewed by the DSMB

The efficacy analyses may be performed on all subjects included in the interim analysis and/or, separately, for AD and/or PD subgroups in this set. Additionally, further analyses of PD-MCI, PD-MD, AD-MCI, and AD-MD subgroups may be undertaken in the efficacy analyses if sufficient subjects are enrolled. A final decision on the populations to be analyzed will be made prior to the

interim analysis based on the number of subjects enrolled with PD or AD, and within the further MCI or MD groups. For example, the Sponsor may elect to exclude a patient population from the interim analysis if the post-dose data are available for fewer than e.g., 25 subjects. The baseline and safety summaries will be performed on all subjects included in the interim analysis regardless of the patient population(s) selected for efficacy analysis.

To produce these outputs, a biostatistician and a statistical programmer from [REDACTED], separate from the primary study team, will be unblinded to treatment assignments and work within a restricted domain inaccessible to all other [REDACTED] members. No additional team members from [REDACTED] or CuraSen will become unblinded until after database lock and release of the live randomization list at the time of study completion. The unblinded statistician will be in attendance during the closed DSMB sessions for the purpose of presenting and interpreting the interim analysis results. Additional information regarding the roles, responsibilities, and objectives for the DSMB will be outlined within a DSMB charter, separate from this SAP.

The final analysis will be performed after the last subject completes their End-of-Study visit or their last scheduled assessment per the Schedule of Events, or the sponsor terminates the study for any reason. The full set of analyses summarized in this SAP will be generated upon final study database lock.

5 ANALYSIS SETS/POPULATIONS

Intent to Treat Set (ITT): All subjects who have signed informed consent and have been randomized to a treatment sequence. Subjects will be analyzed according to the treatment sequence assigned at randomization. The ITT will be the analysis set for disposition and select baseline characteristic analyses.

Safety Set (SAF): All subjects who received at least 1 dose of study drug (either CST-2032 or CST-107 or placebo). Subjects will be reported based on treatment and dose received. The Safety Set will be used for reporting safety analyses.

Full Analysis Set (FAS): All randomized subjects who have taken at least 1 dose of blinded study drug (CST-2032+CST-107 or Placebo). Subjects will be analyzed according to the treatment assigned at randomization. The Full Analysis Set will be used for evaluating the cognitive endpoints, pharmacodynamic endpoints and selected secondary endpoints.

Per-Protocol Set (PPS): A subset of the Full Analysis Set who sufficiently complied with the protocol (i.e., has no protocol deviations labeled as “major”). The Per Protocol Set may be used for selected safety analyses.

Pharmacokinetic Set (PKS): All subjects in the Safety Set who have at least one valid plasma concentration assessment for CST-2032 or CST-107. Subjects will be analyzed according to the treatment received. The PKS will be the analysis set for PK concentration and PK parameter analyses.

6 DATA ANALYSIS CONSIDERATIONS

6.1 General Data Handling

All analyses will be conducted based on SAS 9.4 or higher.

Study data will be recorded in eCRFs for all screened and randomized patients. The EDC vendor for this study is MedNet Solutions.

Unless otherwise stated, all listings will be sorted by disease type, treatment sequence, subject number, and assessment date (and time, if available).

Unless stated otherwise, continuous data will be summarized by disease type, treatment sequence, and overall using n, mean, median, standard deviation (SD), minimum value, and maximum value.

Unless stated otherwise, categorical data will be summarized by disease type, treatment sequence, and overall using frequency counts and percentages. Where applicable, 95% confidence intervals (CIs) will be provided. Unless otherwise stated, the denominator of percentages will be the number of participants in the population/treatment arm or the number with non-missing data.

- The number of missing values will be presented as a separate category with no percentage, but only if one or more subjects are missing data.
- Counts of zero will be presented without percentages.

Relative to the number of digits after the decimal in the raw data, summary statistics will have the following number of digits after the decimal:

- Minimum and Maximum: same number of significant digits as the raw data
- Mean and Median: one additional decimal place to that reported for Minimum and Maximum
- SD or Standard Error (SE): two additional decimal places than the Minimum and Maximum
- Percentages: reported to one decimal place
- P-values will be reported to four decimal places. If the value is below 0.0001 it will be noted as < 0.0001; if the value is above 0.9999 it will be noted as > 0.9999.

Unless otherwise noted, statistical inference will be based on a 5% significance level (i.e. 95% confidence intervals will be produced).

All data up to the time of study completion/withdrawal from the study will be included in the analysis, regardless of duration of treatment.

Numbering for data displays will be based on ICH E3.

6.2 Stratification and Covariates

There are no formal plans for analysis stratification.

6.3 Evaluation of Subgroups

All summaries and analyses will be performed by (PD) and (AD). Select secondary efficacy endpoints will be further analyzed by MCI and MD categories (PD-MCI, PD-MD, AD-MCI, and AD-MC).

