8.8. Analysis of Secondary Endpoints

Differences between CST-2032+CST-107 and placebo in performance in cognitive tasks will be assessed using the FAS. For continuous endpoints, the difference is defined as CST-2032+CST-107 minus placebo except as defined in the SAP (e.g., for certain CANTAB test [PAL, RTI, and SSRT]). Comparisons may be made using a mixed model with factors for disease criteria, treatment, treatment sequence, subject nested in sequence (as a random effect), period, and baseline values as appropriate. Comparisons between treatments may also be compared using the paired t-test and/or nonparametric tests where appropriate and as specified in the SAP. These analyses will be conducted for all subjects in the study and also for each disease subset (PD/AD).

Secondary endpoints related to cognition, physiological symptoms, mood and will be summarized by disease criteria, treatment, treatment sequence and overall using the FAS. Select summaries may be repeated in the PPS. Comparisons between treatments will be performed similarly for all secondary endpoints. All data will be listed.

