8.9. Analysis of Exploratory Endpoints

Subgroup analyses may be conducted after study completion to evaluate whether effects of treatment are influenced by baseline disease characteristics including but not limited to disease activity as determined from relevant disease scales at screening, neurodegenerative biomarkers (such phosphorylated tau, neurofilament light chain, total and phosphorylated tau protein, and amyloid- β (A β) peptides) in plasma, and genetic variants including but not limited to APOE4, LRRK2, and GBA. Additionally, change in average z-score for baseline-deficit cognitive tasks identified for each subject from Cognitive tasks in the CANTAB and other cognitive measures may be evaluated.

All exploratory endpoints will be listed.

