6.4 Multiple Comparisons and Multiplicity

This study is descriptive in nature and informal testing of multiple endpoints may be performed. Given the exploratory nature of the comparisons, no adjustment of Type I error is planned.

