- VRM Free Recall Distinct Stimuli Mean Errors – P1.1-1.3: For each recording of VRMFRDM, a new record will be derived as the value of VRMFRDM subtracted from 18. The parameter decode will be VRMFRDME.
- VRM Delayed Free Recall Distinct Stimuli Errors – P2.1: For each recording of VRMFR21D, a new record will be derived as the value of VRMFR21D subtracted from 18. The parameter decode will be VRMFR21E.
- VRM Delayed Recognition Total Correct Errors – P2.2: For each recording of VRMD22TC, a new record will be derived as the value of VRMD22TC subtracted from 36. The parameter decode will be VRMD22TE.

For all 21 parameters, observed values at each assessment and changes from baseline will be summarized using descriptive statistics on the FAS and PPS. In addition to the descriptive statistic summaries, for each parameter, a mixed effects model approach will be used to evaluate treatment effect. The model will include change from baseline as the dependent variable, baseline as a covariate, treatment sequence, period, timepoint (i.e., Day 1: 3 hrs post-dose, Day 7: 3 hrs post-dose, Day 14: 3 hrs post-dose), disease type, and treatment as fixed effects, and subject as a random effect. The least square means will be summarized, as well as the least square mean difference between treatments, where the corresponding p-value for this LS mean difference will be provided. If there are convergence issues, alternative covariance structures may be used including autoregressive of order 1 (AR1) and compound symmetry (CS). The effect size will be estimated using Cohen's D: difference in means / pooled SD. This analysis will be performed using AD and PD as subgroups, and again using AD-MCI, AD-MD, PD-MCI, and PD-MD as subgroups.

Additionally, using treatment period 1 and treatment period 2 data separately, all 21 parameters will have observed value and change from baseline summarized, and a mixed effects model with change from baseline as the dependent variable, baseline as a covariate, timepoint (i.e., Day 1: 3 hrs post-dose, Day 7: 3 hrs post-dose, Day 14: 3 hrs post-dose), disease type, and treatment as fixed effects, and subject as a random effect will be evaluated. The least square means, least

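### The plan has no treatment-by-disease-type contrast, so no estimate answers the exploratory question of whether response differs between AD and PD

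*SAP*

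**What the plan says.** SAP 3 lists as an exploratory objective: "To evaluate whether baseline disease characteristics impact response to treatment". Protocol 2.1 has the same objective.

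Protocol 8.8 plans the treatment comparison in everyone and by disease: "These analyses will be conducted for all subjects in the study and also for each disease subset (PD/AD)". SAP 6.3 says "All summaries and analyses will be performed by (PD) and (AD)" and adds a further MCI/mild dementia breakdown for selected efficacy endpoints. In SAP 9.2 the CANTAB mixed model has "disease type, and treatment as fixed effects, and subject as a random effect", alongside baseline, sequence, period and timepoint. The other scales use the same form, except that the ADCS-CGIC model has no baseline term. For CANTAB, verbal fluency, DSST and MoCA, SAP 9.2 then says: "This analysis will be performed using AD and PD as subgroups, and again using AD-MCI, AD-MD, PD-MCI, and PD-MD as subgroups". The treatment difference is reported as an LS mean difference with a p-value.

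For the exploratory objective itself, Protocol 8.9 says: "Subgroup analyses may be conducted after study completion to evaluate whether effects of treatment are influenced by baseline disease characteristics". It names no method for this, and SAP 9.3 adds no effect-modification analysis. SAP 6.1 sets the general rule that "statistical inference will be based on a 5% significance level", and SAP 6.4 says "no adjustment of Type I error is planned".

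**The concern.** Whether a characteristic changes response is a question about the difference between two treatment effects. A main effect of disease type adjusts the level of the outcome and says nothing about whether the drug effect differs by disease. Separate subgroup models give two effects and two p-values, but not their difference or its uncertainty. No treatment-by-disease term, heterogeneity test or AD-versus-PD contrast of treatment effects appears in either document.

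The AD and PD results will stand side by side, and SAP 9.2 also draws the cognitive plots separately for the two diseases. If one disease crosses 5% and the other does not, a reader could conclude that the drug works in one and not the other. With small subgroups that pattern is common even when the two effects are identical, and it could steer the choice of population for a later trial.

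**Working it through.** **Nothing to reproduce.** The sample size of approximately 60 is a practical choice (Protocol 8.1, SAP 4.3). The documents give no effect size, SD, power or AD/PD split.

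**Inputs**
- Total N = 60, two-period crossover (documents).
- Two-sided 5% per test, no adjustment (SAP 6.1, 6.4).
- 21 CANTAB parameters (SAP 9.2).
- AD/PD split: assumed 30/30, 40/20 or 45/15.
- True effect d: assumed equal in both diseases, in units of the SD of the within-subject difference, with that SD the same in both.
- Simplification: one within-subject difference per subject instead of repeated timepoints.

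**Step 1. Power within a subgroup of n.** Power = P(|T| > t(0.975, n−2)), with T noncentral t, n−2 df and noncentrality d√n. At n = 30 and d = 0.37, the noncentrality is 0.37 × 5.477 = 2.03 and the critical value is 2.05, so power is 0.499.

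**Step 2. Chance that exactly one disease is significant**, with p1 and p2 the two subgroup powers: p1(1 − p2) + p2(1 − p1). At 30/30 and d = 0.37 this is 2 × 0.499 × 0.501 = 0.50. At 45/15 and d = 0.37 it is 0.680 × 0.736 + 0.264 × 0.320 = 0.58.

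| True effect in both (SD) | 30/30 | 40/20 | 45/15 |
|---|---|---|---|
| 0 | 9.5% | 9.5% | 9.5% |
| 0.2 | 30% | 31% | 31% |
| 0.37 | 50% | 54% | 58% |
| 0.5 | 37% | 45% | 55% |
| 0.8 | 2% | 8% | 18% |

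With no effect anywhere, 21 × 0.095 = 2.0 CANTAB parameters would be expected to be significant in one disease only.

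**Step 3. The direct contrast.** The standard error of the AD-minus-PD difference is √(1/n_AD + 1/n_PD). The 95% half-width is t(0.975, 56) = 2.003 times that. The difference detectable with 80% power comes from the noncentral t with 56 df.

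| Split | SE | 95% half-width | 80% power at |
|---|---|---|---|
| 30/30 | 0.258 | ±0.52 SD | 0.74 SD |
| 40/20 | 0.274 | ±0.55 SD | 0.78 SD |
| 45/15 | 0.298 | ±0.60 SD | 0.85 SD |

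In 100,000 simulated trials per setting at 30/30 with equal effects of 0 to 0.5 SD, the interaction test was falsely positive in 4.9% to 5.1%. Among trials with discordant subgroup results, the interaction was significant in only 9% to 33%, so most discordant pairs would be shown as compatible with equal effects.

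**The case against.** The case against is substantial in four respects.

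- **A reader might infer that AD and PD are only ever tested separately.** They are not. Protocol 8.8 plans an all-subject comparison, and a disease-type fixed effect makes sense only in a pooled fit. What is missing is the interaction or contrast.
- **A reader might infer that the sponsor intends to treat discordant p-values as evidence of differential response.** The documents say no such thing. SAP 4.3 states that a non-significant result is not to be taken as absence of effect, SAP 6.4 calls the study descriptive, and SAP 9 labels all inference exploratory. Discordance becomes an error only if someone draws the conclusion. These cautions stand, but they do not supply the missing estimate, and they do not address the positive claim that one disease responds more than the other.
- **The objective is exploratory, and its analysis is optional.** The characteristics named in Protocol 2.4 and 8.9 and SAP 3 are disease scales and genetic variants, with plasma biomarkers added in the protocol. AD versus PD is not named. The list is explicitly open, however, and disease type is the one characteristic by which the SAP systematically splits the results.
- **The gain in formal testing is small.** The interaction test has low power, and 21 unadjusted interaction tests would yield about one false positive under the null (21 × 0.05 = 1.05). Because the AD and PD groups are disjoint, a reader could also approximate the contrast from the two LS mean differences and their intervals. This supports reporting an estimate with its interval instead of relying on one more p-value. It does not support leaving the calculation to the reader.

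**Conclusion.** The point holds in limited form. For disease type, the plan contains no estimate that answers its own exploratory objective, and the planned subgroup p-values could be misread in place of one. With equal true effects, the chance of a discordant AD/PD pair at 30/30 runs from 9.5% (no effect) up to 50% (0.37 SD) and down to 2% (0.8 SD). At 45/15 it is about 58% at 0.37 SD. The 50% figure is the peak of the curve at 30/30 and should not be quoted as the typical risk.

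These sizes rest on an assumed split, assumed effects on the SD-of-difference scale, a common SD in both diseases and one difference per subject. The absence of the contrast does not depend on any of them. The primary safety objective and the all-subject comparison are unaffected.

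**What to change.** In SAP 9.2, for the cognitive endpoints:

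1. Add treatment-by-disease-type to the all-subject mixed model.
2. Report the AD-minus-PD difference in treatment effect with its 95% CI, labelled exploratory.
3. State that differential effects will not be inferred by comparing subgroup p-values.
4. Drop disease type from models fitted within a single disease, where it is constant.

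Two additions are optional: a treatment-by-severity (MCI/mild dementia) model, and deriving the AD and PD effects from the joint model. The second imposes common baseline, period and variance terms across the diseases, so keeping separate subgroup fits is defensible.

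The cost is one model term and one table row per endpoint, with no new data and no design change. The drawback is imprecision: the interval will be roughly ±0.5 to ±0.6 SD, and an interval that includes zero must not be presented as evidence that the diseases respond alike.
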